3.2 Study population

Lymphoma histologies:

Mantle cell lymphoma

- Biopsy-proven diagnosis of Mantle Cell Lymphoma per the World Health Organization classification criteria
- The diagnosis is to be based on histologic and immunophenotypic criteria and include either immunohistochemical analysis for cyclin D1, cytogenetic analysis be either conventional karyotyping or fluorescence in situ hybridization (FISH) for 9(11;14)(q13;32), or both.
- Patient had met institutional standards for having high-dose consolidative therapy

Non-Mantle cell low grade B cell lymphomas (including SLL/CLL)

- Biopsy-proven diagnosis of lymphoma per the World Health Organization classification criteria
- Patient had met institutional standards for having high-dose consolidative therapy and relapsed disease despite the use of at least one chemotherapeutic agent (single agent Rituximab does not qualify for these histologies)
- Exception for mantle cell lymphoma and high risk SLL/CLL [defined as: del(17p), del (11q), or del(13q) concurrent with an unmutated IGVH status] who received high-dose consolidative therapy in first response are eligible for this protocol.

Transformed lymphoma/DLBCL/High risk DLBCL in first response/PMBCL

- Biopsy-proven diagnosis of lymphoma per the World Health Organization classification criteria
- Patient had met institutional standards for having high-dose consolidative therapy.

Gray Zone Lymphoma in first CR

- Biopsy-proven diagnosis of lymphoma per the World Health Organization classification criteria
- Patient had met institutional standards for having high-dose consolidative therapy.

Hodgkin's Disease

- Biopsy-proven diagnosis of lymphoma per the World Health Organization classification criteria
- Patient had met institutional standards for having high-dose consolidative therapy.

3.2.1 Patient population Patients must have had chemotherapy responsive disease (Partial response or better) before high-dose consolidative therapy. The accrual rate for this study is expected to be 20 patients per year. Assuming a three year recruitment period with a minimum follow-up of one year, 60 patients will give us 85% power to detect a 20% increase in EFS: 49% to 69%. Inclusion and exclusion criteria

Patients must have baseline evaluations performed prior to the first dose of study drug and must meet all inclusion and exclusion criteria. Results of all baseline evaluations, which assure that all inclusion and exclusion criteria have been satisfied, must be reviewed by the Principal Investigator or his/her designee prior to enrollment of that patient. In addition, the patient must be thoroughly informed about all regulatory requirements for informed consent. The written informed consent must be obtained from the patient prior to enrollment.

3.2.2. Inclusion Criteria

- Age \geq 18 years of age
- ECOG performance status \leq 2
- INR \leq 2
- Adequate renal and hepatic function defined as a serum creatinine \leq 2.0mg/dL, total bilirubin \leq 5mg/dL, and AST and ALT $<$ 2.5 ULN. • Platelet count \geq 75 x 10^9 /L
- Hemoglobin \geq 10mg/dL
- ANC \geq 3.0x 10^9 /L
- Fasting serum cholesterol \leq 300 mg/dL OR \leq 7.75 mmol/L and fasting triglycerides \leq 2.5 x ULN. NOTE: In case one or both of these thresholds are exceeded, the patient can only be included after initiation of appropriate lipid lowering medication.
- A willingness to use an accepted and effective method of birth control for sexually active women of childbearing potential during the study and for 8 weeks after the end of study drug treatment.
- Ability to sign informed consent.

Exclusion Criteria

- Patient who have previously received an mTor inhibitor
- Patients who are pre-terminal or moribund
- Patients currently receiving anticancer therapies or who have received anticancer therapies within 4 weeks of the start of Everolimus (including chemotherapy, radiation therapy, antibody based therapy, etc.)
- Uncontrolled diabetes mellitus as defined by HbA1c $>$ 8% despite adequate therapy. Patients with a known history of impaired fasting glucose or diabetes mellitus (DM) may be included, however blood glucose and antidiabetic treatment must be monitored closely throughout the trial and adjusted as necessary
- Chronic treatment with corticosteroids or other immunosuppressive agents. Topical or inhaled corticosteroids are allowed
- Patients who have received live attenuated vaccines within 1 week of start of Everolimus and during the study. Patient should also avoid close contact with others who have

received live attenuated vaccines. Examples of live attenuated vaccines include intranasal influenza, measles, mumps, rubella, oral polio, BCG, yellow fever, varicella and TY21a typhoid vaccines;

- Patients who have a history of another primary solid malignancy, with the exceptions of: non-melanoma skin cancer, and carcinoma in situ of the cervix, uteri, or breast from which the patient has been disease free for ≥ 3 years;
- Patients with a history of non-compliance to medical regimens or who are considered potentially unreliable or will not be able to complete the entire study;
- Patients with active bacterial or fungal infections requiring oral or intravenous antimicrobials are not eligible until resolution of the infection
- Female patients who are pregnant or breast feeding, or of reproductive potential who are not using effective birth control methods. Adequate contraception must be used throughout the trial and for 8 weeks after the last dose of study drug.
-
- Male patients whose sexual partner(s) are WOCBP who are not willing to use adequate contraception, during the study and for 8 weeks after the end of treatment
- Patients with known intolerance to rituximab
- Known history of HIV or Hepatitis C
- Active Hepatitis B as defined by seropositivity for hepatitis B surface antigen. Subjects with positive hepatitis B core antibody titers and normal liver transaminases are allowed provided that prophylaxis is administered per institutional guidelines. Please see Addendum 8 for the action to be taken for patients with positive baseline hepatitis B results.

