Grade 2 (Symptomatic, not interfering with Activities of Daily Living)	CT scan with lung windows. Consider pulmonary function testing includes: spirometry, DLCO, and room air O ₂ saturation at rest. Consider a bronchoscopy with biopsy and/or BAL. Monitoring at each visit until return to \leq grade 1. Return to initial monitoring frequency if no recurrence.	Symptomatic only. Consider corticosteroids and/or other supportive therapy if symptoms are troublesome.	Rule out infection and consider interruption of Everolimus until symptoms improve to Grade \leq 1. Re-initiate Everolimus at one dose level lower. Discontinue Everolimus if failure to recover within \leq 28 days.
Grade 3 (Symptomatic, Interfering with Activities of Daily Living. O ₂ indicated)	CT scan with lung windows and pulmonary function testing includes: spirometry, DLCO, and room air O ₂ saturation at rest. Monitoring at each visit until return to \leq grade 1. Return to initial monitoring frequency if no recurrence. Bronchoscopy with biopsy and/or BAL is recommended.	Consider corticosteroids if infective origin is ruled out. Taper as medically indicated.	Rule out infection and interrupt Everolimus until symptoms improve to Grade \leq 1. Consider re-initiating Everolimus at one dose level lower (approximately 50% lower than the dose previously administered depending on individual clinical circumstances) Discontinue Everolimus if failure to recover within \leq 28 days. If toxicity recurs at Grade 3, consider discontinuation
Grade 4 (Life-threatening, ventilatory support indicated)	CT scan with lung windows and required pulmonary function testing, if possible, includes: spirometry, DLCO, and room air O ₂ saturation at rest. Monitoring at each visit until return to \leq grade 1. Return to initial monitoring frequency if no recurrence. Bronchoscopy with biopsy and/or BAL is recommended if possible.	Consider corticosteroids if infective origin is ruled out. Taper as medically indicated.	Rule out infection and discontinue Everolimus.

Addendum 8: Action to be taken for positive baseline hepatitis B results

Test	Result	Result	Result	Result	Result
HBV-DNA	+	+ or -	-	-	-
HBsAg	+ or -	+	-	-	-
HBsAb	+ or -	+ or -	+ and no prior HBV vaccination	+ or -	- or + with prior HBV vaccination
HBcAb	+ or -	+ or -	+ or -	+	-

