Recommendation	Prophylaxis treatment should be started 1-2 weeks prior to first dose of study drug. Monitor HBV-DNA approximately every 4 weeks		No prophylaxis Monitor HBV-DNA approximately every 4 weeks		No specific action

Antiviral prophylaxis therapy should continue for at least 4 weeks after last dose of study drug.

For patients who have already received study drug prior to the approval of Protocol Version date February 18, 2014, HBV-DNA testing will be performed at the patient's next visit, and the result will be regarded as baseline. Any action for positive hepatitis results will then proceed as detailed in the table above.

Addendum 9: Guidelines for management of hepatitis B

HBV reactivation (with or without clinical signs and symptoms)*	

For patients with baseline results:
 
Positive HBV-DNA OR positive HBsAg
 
-----
 
reactivation is defined as: [Increase of 1 log in HBV-DNA relative to baseline HBV-DNA value OR new appearance of measurable HBV-DNA]
 
AND
 
ALT elevation x 5 ULN
	
Treat: Start a second antiviral AND Interrupt study drug administration until resolution: \leq grade 1 ALT (or baseline ALT, if $>$ grade 1) and \leq baseline HBV-DNA levels
 
If resolution occurs within \leq 28 days study drug should be re-started at one dose lower, if available. If the patient is already receiving the lowest dose of study drug according to the protocol, the patient should restart at the same dose after resolution. Both antiviral therapies should continue at least 4 weeks after last dose of study drug.
 
If resolution occurs $>$ 28 days Patients should discontinue study drug but continue both antiviral therapies at least 4 weeks after last dose of study drug.

For patients with baseline results:
 
Negative HBV-DNA and HBsAg AND Positive HBs Ab (with no prior history of vaccination against HBV), OR positive HBc Ab
 
-----
 
reactivation is defined as: New appearance of measurable HBV-DNA
	
Treat : Start first antiviral medication AND Interrupt study drug administration until resolution: \leq baseline HBV-DNA levels
 
If resolution occurs within \leq 28 days study drug should be re-started at one dose lower, if available. If the patient is already receiving the lowest dose of study drug according to the protocol, the patient should restart at the same dose after resolution. Antiviral therapy should continue at least 4 weeks after last dose of study drug.

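### Core-antibody-positive, HBsAg-negative, HBV-DNA-negative patients may enter only with antiviral prophylaxis under Section 3.2.2, but Addendum 8, to which that criterion refers, recommends none

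*Combined protocol and SAP*

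**What the plan says.** **Section 3.2.2, exclusion list.** The hepatitis B item excludes "Active Hepatitis B as defined by seropositivity for hepatitis B surface antigen". It then lets in patients with positive core antibody and normal transaminases, who are "allowed provided that prophylaxis is administered per institutional guidelines". It closes by referring to Addendum 8 for what to do about positive baseline results. The opening text on eligibility, under Section 3.2.1, makes the list binding: patients "must meet all inclusion and exclusion criteria".

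**Addendum 8.** The table has five columns of baseline results and a recommendation row.
- Columns 1 and 2 (HBV-DNA positive, or HBsAg positive): "Prophylaxis treatment should be started 1-2 weeks prior to first dose of study drug", with HBV-DNA monitoring.
- Columns 3 and 4 (HBV-DNA and HBsAg both negative): "No prophylaxis Monitor HBV-DNA approximately every 4 weeks". Column 3 is HBsAb positive "and no prior HBV vaccination", with HBcAb of either sign. Column 4 is HBcAb positive, with HBsAb of either sign.
- Column 5 (HBcAb negative, and HBsAb negative or explained by vaccination): no specific action.

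**Addendum 9.** On reactivation, the group that was HBV-DNA or HBsAg positive at baseline is told "Start a second antiviral AND Interrupt study drug administration until resolution". The group that was negative for both but antibody positive is told "Start first antiviral medication AND Interrupt study drug administration until resolution".

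**The concern.** A patient with positive core antibody, negative HBsAg and negative HBV-DNA is the typical person the Section 3.2.2 exception is meant for, and that patient receives opposite instructions. The criterion makes prophylaxis a condition of entry; the table it names as the source of action says to give none. Nothing in the protocol ranks one text above the other.

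Two things are at stake. First, following Addendum 8 as written puts a patient on study who does not satisfy a mandatory criterion. Second, it leaves out a measure that Section 3.2.5 describes as lowering the risk of hepatitis B reactivation and its consequences, in a trial of a drug for which the same section reports reactivation. Under Addendum 9 a reactivation interrupts everolimus, ends it if resolution takes more than 28 days, and is recorded as at least grade 3. Section 2.0 judges safety by avoidance of grade III or higher toxicity, so an avoidable reactivation would enter the primary safety data.

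**Working it through.** The plan gives no figure to reproduce. The check is a side-by-side reading.

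**Step 1: whom the exception covers.** HBsAg-positive patients are excluded, so the core-antibody clause applies to HBcAb-positive, HBsAg-negative patients with normal transaminases.

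**Step 2: list their profiles.** Two baseline results remain free: HBV-DNA (positive or negative) and HBsAb (negative, positive without vaccination, positive after vaccination). That gives 2 × 3 = 6 profiles.

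| HBV-DNA | HBsAb | Addendum 8 column | Addendum 8 | Section 3.2.2 | Agree? |
|---|---|---|---|---|---|
| + | negative | 1 | prophylaxis | prophylaxis | yes |
| + | positive, unvaccinated | 1 | prophylaxis | prophylaxis | yes |
| + | positive, vaccinated | 1 | prophylaxis | prophylaxis | yes |
| − | negative | 4 | none | prophylaxis | no |
| − | positive, unvaccinated | 3 and 4 | none | prophylaxis | no |
| − | positive, vaccinated | 4 | none | prophylaxis | no |

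The texts agree in 3 of 6 profiles and conflict in 3 of 6. The dividing line is HBV-DNA status alone.

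**Step 3: rule out a layout artefact.** The recommendation row has merged cells, so the assignment of its entries to columns needs support from elsewhere. Addendum 9 supplies it in running text. For patients negative on HBV-DNA and HBsAg but positive for core antibody, the antiviral begun at reactivation is the first one. In the other group it is the second, because those patients are already on prophylaxis. The addenda therefore assume no prophylaxis in the HBcAb-positive, HBV-DNA-negative group.

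**Step 4: could the criterion leave the decision to local guidelines?** The sentence makes giving prophylaxis the condition. The reference to institutional guidelines governs how it is given, not whether.

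**Step 5: can the monitoring be done within existing visits?** Section 3.4.1 schedules blood every 2 weeks for 60 days and then monthly to one year. Taking days 28 and 56, then every 30 days from day 90 to day 360, gives 2 + 10 = 12 tests. The longest gap is 90 − 56 = 34 days. Exact 4-week testing would give 52/4 = 13. The day grid is an assumption consistent with the schedule.

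**The case against.** The strongest reply is that the documents do not show which text reflects the investigators' intent. Addenda 8 and 9 agree with each other. Addendum 8 is titled as action to be taken and carries a trial-specific rule: patients dosed before approval of the version dated February 18, 2014 have HBV-DNA tested at the next visit and are then managed by the table. The monitoring-only pathway also has safeguards, with HBV-DNA about every 4 weeks and, in this group, antiviral treatment and drug interruption at any new measurable HBV-DNA, with no ALT threshold. The principal investigator or designee reviews every criterion before enrolment, so the prophylaxis condition should be seen. A site can also satisfy both concerns by giving prophylaxis and monitoring as well. Finally, 3 of 6 counts serological combinations, not patients.

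Much of this stands as qualification. Intent is uncertain, so the investigators must confirm the direction of the fix. The statement in Section 3.2.5 about antivirals is general and gives nothing specific to HBV-DNA-negative patients. The profile count says where the conflict lies, not how often it will arise.

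None of it removes the contradiction. The February 2014 rule is transitional, concerns patients already past entry, and does not rank the table above the criterion. Prophylaxis plus monitoring is workable, but the protocol nowhere says to do it. Pre-enrolment review does not settle the matter when the criterion itself directs the reviewer to the conflicting table.

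**Conclusion.** The inconsistency is real and should be fixed. For HBcAb-positive patients with normal transaminases who are negative for HBsAg and HBV-DNA, Section 3.2.2 requires prophylaxis and Addendum 8 recommends against it, in all three HBsAb profiles. HBV-DNA-positive patients are unaffected because both texts call for prophylaxis; HBsAg-positive patients are unaffected because they are excluded. The number of patients concerned is not given and is not estimated here. Sample size, power and the planned analyses do not change.

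The conclusion rests on reading the entry condition as requiring administration and on assigning the no-prophylaxis entry to columns 3 and 4, which Addendum 9 supports independently of the table layout.

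**What to change.** **Preferred change.** Bring the addenda into line with the entry criterion.
- Addendum 8, column 4: replace the entry with prophylaxis per institutional guidelines, keeping the existing HBV-DNA monitoring.
- Addendum 8, column 3: apply the same to HBcAb-positive patients, for example by restricting this column to HBcAb-negative patients, since column 4 already covers the rest.
- Addendum 9: for patients in this group already on prophylaxis, make the step at reactivation the addition of a second antiviral, as in the other group.

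This direction is preferred because the entry criterion is mandatory, while Addendum 8 is a recommendation table that also covers HBsAg-positive patients, whom the trial excludes.

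**Alternative.** If the investigators intend monitoring only, remove the prophylaxis condition from Section 3.2.2 and state that HBV-DNA-negative patients are monitored under Addendum 8.

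**Cost.** This is a wording amendment. Measured against Section 3.2.2, the preferred change adds no treatment. Measured against Addendum 8 as it stands, it adds antiviral therapy through the treatment year and for at least 4 weeks after the last dose. It adds no test beyond those Addendum 8 already calls for, and the scheduled year-1 draws can carry the monitoring without extra visits. An HBV-DNA row in the study calendar would help but is optional, since footnote 6 already points to both addenda.

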3.2.3 Study Interruption or Study Withdrawal

A patient may be taken off this study early or may discontinue participation in this clinical study due to the following factors:

- Serious or intolerable adverse reaction to treatment
- Progression of disease
- Protocol violation
- Withdrawal of consent
- Withdrawal of sponsor support

There is no limit to how long a patient can have their treatment on hold. Prolonged holds are not considered “serious or intolerable adverse reactions to treatment.”

3.2.4 Monitoring of everolimus suspected toxicities: Patients whose treatment is interrupted or permanently discontinued due to an adverse event or abnormal laboratory value suspected to be related to everolimus must be followed at least weekly until the adverse event or abnormal laboratory completely resolves or returns to baseline as clinically appropriate. For patients whose treatment is on hold, labs will be monitored every two weeks while on hold.

3.2.5 Known Undesirable Side Effects of everolimus

Overall, safety data available from completed, controlled and uncontrolled studies indicate that everolimus is generally well tolerated at weekly or daily dose schedules. The safety profile is characterized by manageable adverse events (AEs). These AEs are generally reversible and non-cumulative.

Adverse events most frequently observed with everolimus are stomatitis, rash, diarrhea, fatigue, infections, asthenia, nausea, peripheral edema, decreased appetite, headache, dysgeusia, epistaxis, mucosal inflammation, pneumonitis, weight decreased, vomiting, pruritus, cough, dyspnea, dry skin, nail disorder, and pyrexia. Overall, the most frequently observed laboratory abnormalities include decreased hematologic parameters including hemoglobin, lymphocytes, platelets, and neutrophils (or collectively as pancytopenia); increased clinical chemistry parameters including cholesterol, triglycerides, glucose, aspartate transaminases, creatinine, alanine transaminases, and bilirubin; and decreased clinical chemistry parameters including phosphate and potassium. The majority of these AEs have been of mild to moderate severity (NCI CTC grade 1-2).

Everolimus has immunosuppressive properties and may predispose patients to bacterial, fungal, viral or protozoan infections, including infections with opportunistic pathogens. Localized and systemic infections, including pneumonia, other bacterial infections, invasive fungal infections, such as aspergillosis or candidiasis and viral infections including reactivation of hepatitis B virus, have been described in patients taking everolimus. Some of these infections have been severe (e.g. leading to sepsis, respiratory or hepatic failure) and occasionally have had a fatal outcome.

Physicians and patients should be aware of the increased risk of infection with everolimus. Treat pre-existing infections prior to starting treatment with everolimus. While taking everolimus, be vigilant for symptoms and signs of infection; if a diagnosis of infection is made, institute appropriate treatment promptly and consider interruption or discontinuation of everolimus. If a diagnosis of invasive systemic fungal infection is made, discontinue everolimus and treat with appropriate antifungal therapy.

Reactivation of Hepatitis B (HBV) has been observed in patients with cancer receiving chemotherapy (Yeo 2004). Sporadic cases of Hepatitis B reactivation have also been seen in this setting with everolimus. Use of antivirals during anti-cancer

therapy has been shown to reduce the risk of Hepatitis B virus reactivation and associated morbidity and mortality (Loomba 2008). A detailed assessment of Hepatitis B/C medical history and risk factors must be done for all patients at screening, with testing performed prior to the first dose of everolimus. Addendum 8 details the action to be taken for a patient with a positive baseline hepatitis B result. For hepatitis B reactivation, definition, and management guidelines, please see Addendum 9. For patients who have already received study drug prior to the approval of Protocol Version date February 18, 2014, HBV-DNA testing will be performed at the patient's next visit, and the result will be regarded as baseline.

Hypersensitivity reactions manifested by symptoms including, but not limited to, anaphylaxis, dyspnea, flushing, chest pain or angioedema (e.g. swelling of the airways or tongue, with or without respiratory impairment) have been observed with everolimus.

Hyperglycemia has been reported in clinical trials. Monitoring of fasting serum glucose is recommended prior to the start of everolimus therapy and periodically thereafter. Optimal glycemic control should be achieved before starting a patient on everolimus. Mouth ulcers, stomatitis and oral mucositis have been seen in patients treated with everolimus. In such cases topical treatments are recommended, but alcohol- or peroxide-containing mouthwashes should be avoided as they may exacerbate the condition. Antifungal agents should not be used unless fungal infection has been diagnosed.

Cases of renal failure (including acute renal failure), some with fatal outcome, occurred in patients treated with everolimus. Renal function of patients should be monitored particularly where patients have additional risk factors that may further impair renal function. Elevations of serum creatinine, usually mild, have been reported in clinical trials. Monitoring of renal function, including measurement of blood urea nitrogen (BUN), urinary protein, or serum creatinine, is recommended prior to the start of everolimus therapy and periodically thereafter.

Decreased hemoglobin, lymphocytes, platelets and neutrophils have been reported in clinical trials. Monitoring of complete blood count is recommended prior to the start of everolimus therapy and periodically thereafter.

Everolimus is not recommended in patients with severe hepatic impairment, (Child-Pugh class C).

The use of live vaccines and close contact with those who have received live vaccines should be avoided during treatment with everolimus.

Hypophosphatemia, hypomagnesemia, hyponatremia and hypocalcemia have been reported as serious adverse reactions. Electrolytes should be monitored in patients treated with everolimus.

Addendums 4-7 provide recommendations for the management of patients, with suspected drug toxicities while on treatment with everolimus.

More detailed information regarding everolimus reported suspected toxicities and individual cases is provided in the Investigator's Brochure. Management of non-infectious pneumonitis is described in Addendum 7.

